6.2 Analysis Populations

The full analysis set (FAS) will include all randomized patients.

The per-protocol set (PPS) will include all randomized patients who have received 24 weeks treatment with a study dialyzer without missing 3 consecutive study treatments (i.e. missing a full week of dialysis sessions) and do not have any major protocol violations that might impact the primary analyses.

The primary analyses will be performed on the FAS and supported by an analysis using the PPS. All other analyses will be performed on the FAS unless otherwise noted.

FAS is presented as-treated for analyses of

• AEs, SAEs, and Product Complaints

For other analyses including primary, secondary and exploratory endpoints, FAS is presented as-randomized.

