7.2.2 Primary Analysis

The primary analyses will be performed using a multiple imputation approach. Multiple imputations using SAS Proc MI will be implemented to impute missing data under the missing at random assumption and the data sets generated will be analyzed using SAS Proc MIANALYZE.⁹

The multiply imputed data sets are then analyzed by using standard procedures for complete data and combining the results from these analyses. Multiple imputation does not attempt to estimate each missing value through simulated values, but rather to represent a random sample of the missing values. This process results in valid statistical inferences that properly reflect the uncertainty due to missing values.

Multiple imputation inference involves three distinct phases:

- 1. The missing data are filled in m times to generate m complete data sets.
- 2. The m complete data sets are analyzed by using standard procedures.
- 3. The results from the m complete data sets are combined for the inference.

The MI procedure is a multiple imputation procedure that creates multiply imputed data sets for incomplete p-dimensional multivariate data. It uses methods that incorporate appropriate variability across the m imputations. The imputation method of choice depends on the patterns of missingness in the data and the type of the imputed variable.

A data set with variables Y_1, Y_2, \ldots, Y_p (in that order) is said to have a monotone missing pattern when the event that a variable Y_j is missing for a particular individual implies that all subsequent variables $Y_k, k > j$, are missing for that individual.

For data sets with monotone missing patterns, the variables with missing values can be imputed sequentially with covariates constructed from their corresponding sets of preceding variables. The regression method (Rubin 1987, pp. 166-167)¹⁰ for imputation will be used. Using the primary safety analysis as an example, if a subject is missing serum albumin values at weeks 20 and 24, a regression model is first fitted using the non-missing values prior to week 20 (baseline, weeks 4, 8, 12, and 16) in order to impute the missing value for week 20. This method is then repeated in order to impute the missing value for week 24 using the non-missing values of the prior weeks plus the newly imputed value for week 20.

Twenty (20) complete data sets will be analyzed for the multiple imputation of the primary endpoint data.

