9.3 Clinical Laboratory Evaluations

- Date and time lab sample collected (listing only)
- Initial / re-test (listing only)
- Accession / sample number (listing only)

Table 7: List of Laboratory Tests

(Test on screening pre-dialysis):

- β-hCG (if applicable)
- Hepatitis A, B and C
- Human Immunodeficiency Virus

(Test on screening pre-dialysis, 1st treatment day pre-dialysis, week 4 pre-/post-dialysis and week 24 pre-/post-dialysis):

- λ FLC
- κ FLC

(Test on 1st treatment day pre-dialysis, week 4 pre-/post-dialysis and week 24 pre-/post-dialysis):

- β2-microglobulin
- CFD
- IL-6
- TNFα

(Test on 1st treatment day pre-dialysis, week 12 predialysis, week 24 pre-dialysis and end of study predialysis):

- Factor II
- Factor VII
- Protein C

(Test on 1st treatment day pre-dialysis, week 4 pre-dialysis, week 24 pre-dialysis and end of study pre-dialysis):

• Vitamin A

(Test on every visit pre-dialysis besides end of study pre-dialysis):

• hs-CRP

Serum Chemistry: (Test on every visit pre-dialysis):

• Albumin

(Test on every visit pre-/post-dialysis besides 1st treatment day and end of study):

• BUN

(Test on screening pre-dialysis, 1st treatment day pre-dialysis, week 12 pre-dialysis and end of study pre-dialysis):

• Phosphorus

Coagulation (test on screening pre-dialysis, week 12 pre-dialysis and end of study pre-dialysis):

- Prothrombin time
- INR
- Activated partial thromboplastin time

Comprehensive Metabolic Panel (test on screening pre-dialysis, 1st treatment day pre-dialysis, week 12 pre-dialysis and end of study pre-dialysis):

• Bicarbonate

Hematology (test on screening pre-dialysis, 1st treatment day pre-dialysis, week 12 pre-dialysis and end of study pre-dialysis):

- Calcium
- Chloride
- Creatinine
- Glucose
- Sodium
- Potassium

Liver Function (test on screening pre-dialysis, week 12 pre-dialysis and end of study pre-dialysis):

- Alkaline phosphatase
- ALT; SGPT
- AST; SGOT
- Direct bilirubin
- Gamma-glutamyl transferase
- Globulin
- Total bilirubin
- Total protein

- Hematocrit
- Hemoglobin
- Mean corpuscular hemoglobin
- Mean corpuscular hemoglobin concentration
- Mean corpuscular volume
- Platelet count
- Red blood cell count
- White blood cell count with differential

Lipids (test on screening pre-dialysis, 1st treatment day pre-dialysis, week 12 pre-dialysis and end of study pre-dialysis):

- Total cholesterol
- HDL cholesterol
- LDL cholesterol
- Triglycerides

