12.3 Secondary Analysis

The analysis of the secondary efficacy endpoints will be carried out on the FA.

In order to account for multiplicity, secondary efficacy analyses will be held to a hierarchical assessment and performed in the order outlined below. If the first analysis results in a p-value <0.05, then formal testing will continue to the second analysis. If the second analysis also results in a p-value <0.05, then formal testing will continue to the third analysis, and so on. This method of hierarchical assessment will continue until an analysis results in a p-value > 0.05, i.e., is considered statistically insignificant. This hierarchical approach guarantees that the overall alpha will not exceed 0.05.

- 1. MMRM of reduction ratio of λ FLC
- 2. MMRM of reduction ratio of CFD
- 3. MMRM of reduction ratio of κ FLC
- 4. MMRM of reduction ratio of IL-6
- 5. MMRM of reduction ratio of TNFα
- 6. MMRM of reduction ratio of β 2-microglobulin
- 7. ANCOVA of change in pre-dialysis β 2-microglobulin from baseline to 24 weeks
- 8. MMRM of Kt/Vurea

An MMRM model will be used to evaluate differences between treatment groups in the reduction ratios of λ FLC, CFD, κ FLC, IL-6, TNF α , β_2 -microglobulin after 4 weeks and after 24 weeks of treatment. The model will include the fixed effect of treatment, visit, and the random effect of patient.

An ANCOVA with a fixed effect of treatment and a fixed continuous effect of baseline pre-dialysis β_2 -microglobulin will be used to evaluate differences between treatment groups for the change from baseline in pre-dialysis β_2 -microglobulin after 24 weeks of treatment.

An MMRM model will be used to evaluate differences between treatment groups in Kt/V_{urea} collected after each 4 weeks of treatment. The model will include the fixed effect of treatment, visit, and the random effect of patient.

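### Step 7 of the secondary hierarchy (change in pre-dialysis β2-microglobulin) has no missing-data method, so a full-analysis-set test loses patients without a Week 24 value and leaves scheduled Week 4 values unused

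*SAP*

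**What the plan says.** - **The test.** SAP 12.3 lists step 7 as "ANCOVA of change in pre-dialysis β 2-microglobulin from baseline to 24 weeks". The model is "An ANCOVA with a fixed effect of treatment and a fixed continuous effect of baseline" pre-dialysis β2-microglobulin. Protocol 10.6.2 gives the same model.
- **The analysis set.** SAP 12.3: "The analysis of the secondary efficacy endpoints will be carried out on the FA". SAP 6.2: "The full analysis set (FAS) will include all randomized patients".
- **Missing data.** SAP 7.2.2: "The primary analyses will be performed using a multiple imputation approach". The observed-data and LOCF sensitivity analyses in SAP 7.2.3 are likewise confined to the primary analyses. Nothing is stated for step 7.
- **Sampling.** SAP 9.3, Table 7, for β2-microglobulin: "Test on 1st treatment day pre-dialysis, week 4 pre-/post-dialysis and week 24 pre-/post-dialysis". The End of Study visit is not among its sampling times.
- **The other formal steps.** Steps 1 to 6 are MMRMs at Weeks 4 and 24. Step 8 (Kt/V) is an MMRM of values "collected after each 4 weeks of treatment". In each case, "The model will include the fixed effect of treatment, visit, and the random effect of patient".

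**The concern.** A single-visit ANCOVA without imputation can use only patients who have that visit's value, so the analysed group is smaller than the set to which SAP 12.3 assigns the analysis. No other rule in the plan brings the missing patients back:

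- The SAP 5.2 fallback to the End of Study value cannot work for β2-microglobulin, because it is not sampled at that visit. Patients who terminate early are asked for End of Study procedures (protocol 8.6), so they gain no later value either.
- SAP 7.2.1 does not allow a Week 24 session to be collected late.

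Many of these patients would have a pre-dialysis Week 4 value, which carries information about Week 24 beyond baseline. Ignoring it costs some precision. It also removes protection against bias if leaving the study depends on the Week 4 level differently in the two arms. Step 7 carries a formal p-value and decides whether Kt/V is tested.

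**Working it through.** **1. The plan's own figures.** Inputs from SAP 5.3 and 11.1: margin 1.765, SD 3.7, one-sided alpha 0.025, power 80%, dropout 15%.
- Normal approximation: n per arm = 2 × [3.7 × (1.960 + 0.842) / 1.765]² = 68.98, so 69. The t-test needs 70, which gives 80.02% power.
- 70 / 0.85 = 82.4, so 83 per arm and 166 in total. The plan's figures reproduce.

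**2. Patients affected.**
- Without Week 24 at the planned allowance: 166 − 140 = 26 (15.7%).
- When they leave is not given, so two cases are assumed. If dropout is uniform over 24 weeks, 26 × (1 − 4/24) = 21.7, about 22 (13%), have a Week 4 value. If a third leave before Week 4, 26 × 2/3 = 17.3, about 17 (10%), have one.

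**3. Precision.** With monotone missingness, the variance of an arm's Week 24 mean when Week 4 is used is s²[(1 − ρ²)/n24 + ρ²/n4]. Here ρ is the baseline-adjusted correlation of Week 4 with Week 24, n24 = 70 per arm, and n4 is the number with a Week 4 value. The documents do not give ρ. If all three pairwise correlations were 0.8, ρ = (0.8 − 0.64)/(1 − 0.64) = 0.44. Then, with n4 = 83, 1/[(1 − 0.1975)/70 + 0.1975/83] = 72.2 effective patients per arm.

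The documents give no effect size for this endpoint, so power is shown for a difference that the planned ANCOVA, with 70 per arm, would detect with 80% power:

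| ρ | Effective n per arm, all dropout after Week 4 | Power | Power if a third leave before Week 4 |
|---|---|---|---|
| 0.3 | 71.0 | 80.6% | 80.4% |
| 0.44 | 72.2 | 81.2% | 80.9% |
| 0.5 | 72.9 | 81.5% | 81.1% |
| 0.7 | 75.8 | 83.0% | 82.1% |
| 0.8 | 77.8 | 84.0% | 82.8% |
| 0.9 | 80.2 | 85.0% | 83.5% |

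With no missing data (83 per arm) power would be 86.2%.

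**4. Bias, under an assumed mechanism.** Simulation with 83 per arm, no true difference and all pairwise correlations 0.8. In one arm dropout depends on the Week 4 residual (log-odds 0.5 or 1.0 per residual SD); in the other it is random.
- With 15% dropout in both arms, the complete-case bias is about 0.02 SD at slope 0.5 and 0.03 to 0.04 SD at slope 1.0.
- With dropout of about 13% in the control arm and somewhat more in the Theranova arm, where it is selective, the bias is 0.021 and 0.053 SD against a standard error of 0.11. That is 0.19 and 0.48 standard errors, and two-sided rejection would be about 5.4% and 7.7% instead of 5%.
- Using Week 4 brings the bias to within 0.003 SD of zero in every case.
- Making the control arm the selective one reverses the sign.

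**5. A comparison inside the SAP.** Vitamin A is sampled pre-dialysis on Day 1, at Week 4 and at Week 24 (and additionally at End of Study). SAP 11.3 analyses its change from baseline by an MMRM at Weeks 4 and 24 with a baseline covariate. Pre-dialysis β2-microglobulin shares the Day 1, Week 4 and Week 24 schedule but has the single-visit model.

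**The case against.** The strongest defence is that the model matches the endpoint. SAP 5.7 defines this endpoint by the first treatment day and Week 24 only, whereas steps 2 to 6 and Vitamin A are defined at Weeks 4 and 24. A baseline-adjusted ANCOVA is a standard analysis of change, and protocol and SAP agree on it. That stands: the ANCOVA is not invalid, and the choice need not be an oversight. It does not say what happens to patients without Week 24, and Week 4 can inform the Week 24 estimate without becoming part of the endpoint.

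Stronger readings are tempting, and the documents do not support them:

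- *That the other seven steps use the Week 4 value step 7 ignores.* They use Week 4 data on their own variables. Only step 6 uses Week 4 β2-microglobulin, and as a reduction ratio.
- *That 15% of the full analysis set is lost and recoverable.* The 15% is a planning allowance. Patients who leave before Week 4 have no such value.
- *That the SAP prescribes complete cases.* It does not say so; that follows from a single-visit model with no imputation.
- *That step 7 is biased towards Theranova.* This needs dropout related to the Week 4 value and differing by arm. The withdrawal reasons in protocol 4.5 include transplant, switch to PD, change of center and death, and none is tied to β2-microglobulin. Open-label treatment and discretionary withdrawal make arm-dependent dropout possible but do not establish it. If dropout depends only on arm and baseline, and the linear baseline model is right, the planned ANCOVA is unbiased.
- *That the remedy is the procedure already used in the other steps.* Those models have no treatment-by-visit term.

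Little depends on step 7: it is reached after six significant results, and only Kt/V follows it.

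**Conclusion.** The point holds as a modest weakness. Step 7 names the full analysis set but in effect analyses only patients with a Week 24 value, and it leaves unused a scheduled Week 4 value for roughly 10 to 13% of that set at the planned dropout.

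The cost is about 1 point of power at ρ near 0.44, and 0.6 to 5 points over ρ from 0.3 to 0.9 if all dropout follows Week 4, slightly less otherwise. The possible bias of 0.02 to 0.05 SD rests wholly on the assumed dropout mechanism, and its direction is unknown. The sample size is not in error and the primary conclusions are unaffected. Without arm-specific selective dropout, the planned test does not inflate type I error.

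**What to change.** Either of two changes to SAP 12.3 would do:

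- Run step 7 as an MMRM of change in pre-dialysis β2-microglobulin at Weeks 4 and 24, with treatment, visit, treatment-by-visit, baseline and baseline-by-visit, and test the Week 24 contrast.
- Multiply impute Week 24 within arm from baseline and Week 4, then fit the planned ANCOVA.

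Both keep the Week 24 endpoint, the order of the hierarchy and its alpha, and need no new sampling. The MMRM wording used for the other steps should not be carried over: without treatment-by-visit it would test an effect averaged over Weeks 4 and 24.

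The cost is a few lines of SAP text, a slightly more complex model and reliance on missing at random. The planned ANCOVA on observed data can stay as a sensitivity analysis, and the SAP should state how many patients it includes.

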3.4 Study Duration and Dates

Patients will undergo 3 dialysis sessions per week, for 24 weeks. The participating patients should continue with their pre-study HD prescriptions (in terms of treatment time, blood flow rate and dialysate flow rate) and prescriptions should be kept stable throughout the study.

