Appendix 1 Schedule of Evaluations and Procedures

Evaluation	Screening Visit Days - 14 to - 1	Treatment Period														End of Study Visit	
		Visit 1 1 st Treatment Day		Visit 2 Week 4		Visit 3 Week 8		Visit 4 Week 12		Visit 5 Week 16		Visit 6 Week 20		Visit 7 Week 24			
		Pre-dialysis	Post-dialysis	Pre-dialysis	Post-dialysis	Pre-dialysis	Post-dialysis	Pre-dialysis	Post-dialysis	Pre-dialysis	Post-dialysis	Pre-dialysis	Post-dialysis	Pre-dialysis	Post-dialysis		
Informed consent	X																
Demographics	X																
Medical histories (past and present)	X																
Physical examination including weight ^a	X															X	
Vital Signs	X	X	X	X	X	X	X	X	X	X	X	X	X	X	X	X	
Randomization ^b	X																
AE/SAE/ADE/PC ^c	X	X	X	X	X	X	X	X	X	X	X	X	X	X	X	X	
Concomitant medications ^d	X	X	X	X	X	X	X	X	X	X	X	X	X	X	X	X	
HD prescription and Ultrafiltration ^e	X		X		X		X		X		X		X		X		
Body weight	X	X	X	X	X	X	X	X	X	X	X	X	X	X	X	X	
Laboratory Evaluations ^f	X	X		X	X	X	X	X	X	X	X	X	X	X	X	X	
Patient Reported outcomes ^g			X						X						X		

Note: All sampling visits will be performed during the mid-week treatment

^a Weight will be measured at screening and end of study, height will be measured only at screening

^b Eligible patients will be randomized at the end of the Screening Period

^c AEs, SAEs and PCs will be collected after the informed consent is signed and throughout the study, until the end of study visit ADEs will be collected throughout the treatment period

^d Medications will be collected throughout the study

^e Ultrafiltration (UF) will be obtained at the end of treatment of each 4 week treatment period

^f Collection of laboratory samples is presented in the Schedule of Clinical Laboratory Evaluations below

^g Patient reported outcomes (PROs) will include KDQOL-36 and EQ-5D-5L. All PROs will initially be assessed during the first treatment day, after 12 weeks of treatment and at the end of the study, following 24 weeks of treatment

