5.2 Baseline Definition

Baseline measure for laboratory assessments and vital signs is defined as the last predialysis non-missing value obtained prior to dialysis on the day of the first study treatment. The final measure for laboratory assessments is defined as the last value captured during study treatment sessions (Week 24). If laboratory assessment on Week 24 is not applicable, the value on end of study visit (pre-dialysis) will be considered as final measurement.

Baseline measure for demographics, physical examination, general medical history and renal medical history is obtained during screening.

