11.3 Secondary Analysis

The analysis of the secondary safety endpoints will be carried out on the FAS.

Pre-dialysis serum albumin:

A Mixed-effect Model Repeated Measurement (MMRM) model will be used to evaluate differences between treatment groups in the change from baseline in pre-dialysis serum albumin after each four weeks of treatment. The model will include the fixed effect of treatment and visit; the continuous, fixed covariate of baseline measurement; and the random effect of patient.

Pre-dialysis serum albumin will be further categorized at baseline and final measurement into 4 categories: $< 3.5, \ge 3.5-3.9, \ge 4.0-4.4, \ge 4.5$. Shift tables will be generated to cross tabulate the number of patients within each category by treatment.

Pre-dialysis Factor VII, Protein C, Vitamin A, and Factor II:

An MMRM model will be used to evaluate the differences between treatment groups in the change from baseline in pre-dialysis Factor VII, Protein C, Vitamin A, and Factor II after 4 weeks and after 24 weeks of treatment. The model will include the fixed effect of treatment, visit; the continuous, fixed covariate of baseline measurement; and the random effect of patient.

nPNA (nPCR):

An MMRM model will be used to evaluate differences between treatment groups in nPNA(nPCR) collected after each 4 weeks of treatment. The model will include the fixed effect of treatment, visit, and the random effect of patient.

AEs, SAEs, and Product Complaints:

The summary of AEs will include AEs that occur on the day of or after the first study treatment. AEs will be mapped to a Primary SOC and PT according to MedDRA and summarized descriptively by SOC, PT and treatment group. Treatment group comparability in the incidence and incidence rates of adverse events will be evaluated using Fisher's exact test and Wald's method with normal approximation, respectively.¹⁶ AEs that occur prior to 1st day of study treatment will only be listed.

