An overview (overall) summary table of all AEs will be generated that includes the total number of AEs, number and percentage of patients with at least one AE, number and percentage of patients with at least one SAE, number and percentage of patients with at least one AE probably associated with study treatment, number and percentage of patients with an AE leading to study discontinuation and number and percentage of patients with an AE leading to death. This summary table will be presented by treatment group and combining both groups (Total).

Furthermore, separate AE summary tables will be provided by SOC and PT for SAEs and AEs leading to study withdrawal. Separate AE summary tables will be provided to show a breakdown of AEs by SOC, PT and

- a. severity (mild, moderate or severe),
- a. relationship to study treatment ("probably related", "possibly related", and "unable to determine" will be categorized as "related to study treatment" while "unlikely related" and "not related" will be categorized as "unrelated to study treatment").

Study dialyzer related product complaints will be summarized descriptively by study dialyzer.

Chemistry and hematology:

Mean differences between treatment groups in the change from baseline to week 24 predialysis measure (if not applicable, end of study pre-dialysis measure will be used) in chemistry and hematology laboratory tests will be analyzed using an ANCOVA with a fixed effect of treatment and a fixed continuous covariate of baseline laboratory value. BUN will be analyzed in the change from pre-dialysis at screening to pre-dialysis after 24 weeks of treatment; further by BUN reduction ratio as compare to from screening to after 24 weeks of treatment.

The Investigator will receive the laboratory results directly from the central laboratory for review and signature. The Investigator will be notified of any laboratory value that is outside of the normal range, as defined by the laboratory. If a clinically significant change from Screening or the previous visit occurs for any laboratory value and results in medical intervention, as judged by the Investigator, the laboratory abnormality will be recorded as an AE on the eCRF. The Clinical Laboratory Evaluations eCRF page will capture and reconcile with the electronic laboratory data transfer, the sample date and time, test accession number, and if the test is an initial or re-test.

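### The Kt/V and nPNA models use no pre-randomization covariate although pre- and post-dialysis BUN is drawn at screening, which costs precision but causes no bias

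*SAP*

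**What the plan says.** **Models.** SAP 12.3 compares the arms on "Kt/V_{urea} collected after each 4 weeks of treatment. The model will include the fixed effect of treatment, visit, and the random effect of patient". SAP 11.3 does the same for "nPNA(nPCR) collected after each 4 weeks of treatment. The model will include the fixed effect of treatment, visit, and the random effect of patient". The protocol (10.6.1 and 10.6.2) specifies the same terms. Kt/V is item 8 of 8 in the fixed testing sequence; nPNA is a secondary safety endpoint outside it.

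**Other models.** A baseline covariate is included for albumin, the coagulation factors, vitamin A, chemistry and hematology (SAP 11.3), the change in pre-dialysis β2-microglobulin (SAP 12.3) and hs-CRP (SAP 13).

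**Sampling.** SAP 9.3, Table 7, schedules BUN as follows: "Test on every visit pre-/post-dialysis besides 1st treatment day and end of study". Screening therefore has a pre/post pair and Day 1 has none (also SAP Table 2 and Protocol Appendix 2). Randomization comes at the end of screening.

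**Baseline.** SAP 5.2 defines the laboratory baseline as the value "obtained prior to dialysis on the day of the first study treatment". For BUN no such sample exists. SAP 11.3 makes its own exception: "BUN will be analyzed in the change from pre-dialysis at screening to pre-dialysis after 24 weeks of treatment", and it also compares the BUN reduction ratio from screening to week 24.

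**The concern.** Treatment varies between patients, not within them. The random patient effect accounts for the correlation among a patient's six visits, but it does not take between-patient variance out of the contrast between arms. Only a covariate related to the outcome can do that.

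Such a covariate is collected. It should carry some information on later values, because patients enter after at least three months of high-flux dialysis and Protocol 3.4 says that "prescriptions should be kept stable throughout the study". Randomization is stratified by site alone, so a chance imbalance in starting dialysis dose or pre-dialysis BUN would stay in the estimate.

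At stake is the width of the interval for dialysis adequacy, a stated secondary objective, and for protein catabolic rate, a safety measure for which a wide interval can conceal a difference.

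**Working it through.** **The plan's own figures.** The documents give no SD, correlation, effect size or power for Kt/V or nPNA. The only usable figure is 70 evaluable patients per arm, from the albumin calculation (SAP 5.3). It reproduces:
- Normal approximation: 2 × (1.960 + 0.842)² × 3.7² / 1.765² ≈ 69 per arm.
- Noncentral t at 70 per arm: 80.02% power.
- Dropout: 70 / 0.85 = 82.4, so 83 per arm and 166 in total.

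**Inputs for this point**
- Visits: 6 (weeks 4, 8, 12, 16, 20 and 24).
- ρ: correlation between any two study visits (assumed).
- s: correlation of the screening covariate with a study visit (assumed). With two covariates, as for nPNA, s² stands for the squared multiple correlation of a single visit with both.
- Total SD set to 1, complete data, treatment effect averaged over visits.

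**Formulas**
- Per-patient variance behind the contrast, no covariate: V0 = (1 + 5ρ)/6.
- With the screening covariate: V1 = V0 − s².
- Variance cut: s²/V0. Interval width relative to no covariate: √(V1/V0).
- Difference detectable with 80% power, two-sided 0.05, 70 per arm: 2.802 × √(2V/70), in SD units.

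| ρ | s | V0 | V1 | Variance cut | Relative width | Detectable difference, before → after |
|---|---|---|---|---|---|---|
| 0.3 | 0.3 | 0.417 | 0.327 | 22% | 0.89 | 0.31 → 0.27 |
| 0.5 | 0.3 | 0.583 | 0.493 | 15% | 0.92 | 0.36 → 0.33 |
| 0.5 | 0.5 | 0.583 | 0.333 | 43% | 0.76 | 0.36 → 0.27 |
| 0.7 | 0.3 | 0.750 | 0.660 | 12% | 0.94 | 0.41 → 0.38 |
| 0.7 | 0.5 | 0.750 | 0.500 | 33% | 0.82 | 0.41 → 0.33 |
| 0.7 | 0.7 | 0.750 | 0.260 | 65% | 0.59 | 0.41 → 0.24 |

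Example: at ρ = 0.7, V0 = (1 + 3.5)/6 = 0.75; with s = 0.5 the cut is 0.25/0.75 = 33%. Between-patient variance makes up ρ/V0 = 0.7/0.75 = 93% of the unadjusted contrast variance, so averaging over six visits helps little.

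**Check.** In 4,000 simulated trials with s = ρ, the variance cut was 41% at 0.5 and 66% at 0.7, against 43% and 65% by formula.

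**Which screening quantities are assured.** The SAP Appendix 1 formulas need the following:

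| Input | At screening |
|---|---|
| Pre- and post-dialysis BUN | Scheduled |
| Session time | Protocol 8.4.1 places treatment parameters at treatment visits; Protocol 6.2 records only a mean pre-study duration |
| Ultrafiltration | Row marked at screening in Protocol Appendix 1, but footnote e names only the 4-week treatment periods |
| Weight | "Weight will be measured at screening and end of study, height will be measured only at screening", with one screening column and no pre/post split |

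Only the BUN pair is certain. For nPNA, the Appendix 1 formula is driven by pre-dialysis BUN as well as by spKt/V, so the post/pre ratio alone would lose part of the information.

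**The case against.** The strongest reply is that nothing is wrong with the planned analysis. It is a valid randomized comparison, and it matches endpoints defined as values after every four weeks with no baseline component. The models that do adjust mostly concern analytes with a Day 1 sample that fits SAP 5.2; BUN has none. That stands: the difference between models follows from the sampling schedule and is not in itself a contradiction. It does not answer why a pre-randomization measurement that SAP 11.3 already treats as the reference for BUN goes unused here.

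Three stronger readings are tempting, and the documents do not support them.
- **That the results would be biased or the error rate inflated.** They would not. A chance imbalance left unadjusted is part of the ordinary sampling error that the interval already covers.
- **That screening Kt/V and nPNA can simply be calculated from data in hand.** Session time, ultrafiltration and post-dialysis weight at the screening session are not assured. Using the full value where available and the BUN ratio elsewhere would combine two scales that run in opposite directions.
- **That the gain is known to be large.** The highest figures assume that screening correlates with study visits as strongly as study visits do with one another. Screening is on the previous high-flux dialyzer, whose model is not specified, and Protocol 5.3 lets session duration vary with clinical need. A screening correlation below ρ is therefore plausible.

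The consequence is also limited. Kt/V is formally tested only if steps 1 to 7 succeed, and neither endpoint has a margin, power target or decision rule.

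**Conclusion.** The point holds as a loss of precision in two secondary analyses. Over the correlations shown, adjustment would cut the contrast variance by between 12% and 65%, that is, an interval 6% to 41% narrower. The middle cases are 33% (ρ = 0.7, s = 0.5; interval 18% narrower) and 43% (both 0.5; interval 24% narrower). These figures rest on assumed correlations, equal correlation between study visits and complete data at 70 per arm. The primary endpoints are unaffected. Priority is low to moderate.

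**What to change.** Amend the SAP before treatment-level results are seen.
- **12.3, item 8:** add the screening post/pre BUN ratio as a continuous covariate in the Kt/V model.
- **11.3, nPNA:** add the screening pre-dialysis BUN and the screening post/pre BUN ratio.
- **5.2:** state that, for these two models, the reference is screening, as an exception to the Day 1 definition.
- **Alternative covariate:** use the screening Kt/V and nPNA from Appendix 1 instead only if session time, ultrafiltration and post-dialysis weight are confirmed as recorded at the screening session for all patients. Use one measure for everyone; do not mix the two within one covariate.
- **Missing screening values:** keep these patients in the full analysis set, for example by imputing the covariate with its mean pooled over both arms.

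The cost is one or two extra model terms, one simple derived variable and a few lines of SAP text. No new data are needed for the BUN-based covariates.
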